3. To identify clinic-level barriers to adoption and implementation of 3HP under each delivery strategy.
4. To determine the proportion of patients for whom 3HP treatment is discontinued due to adverse events/intolerance.
5. To determine the cumulative 16-month incidence of active TB in each arm.
6. To determine the cumulative 28-month incidence of active TB in each arm.

Study Design:

Participants will be randomized to one of three arms to receive latent tuberculosis infection (**LTBI**) treatment with once weekly isoniazid (INH) and rifapentine (RPT) for 12 weeks given by either facilitated DOT, facilitated SAT, or an informed choice between DOT and SAT (with the assistance of a decision aid tool).

Study Agents:

Participants in all arms will receive the following medications approved for TB preventive therapy by the World Health Organization (**WHO**):

- RPT 900 mg and INH 900 mg once-weekly x 12 doses
- Pyridoxine (vitamin B₆) 50 mg offered once weekly, as recommended for 3HP, to protect against isoniazid-related peripheral neuropathy

Study Population/Sample Size:

We will enroll 1656 PLHIV (552/arm) aged 18 years and above accessing HIV/AIDS care at the Mulago Immune Suppression Syndrome Clinic who meet all study inclusion criteria and none of the exclusion criteria.

Outcomes:

1. Primary Outcome:

- The proportion of eligible participants who accept treatment and take at least 11 of 12 once weekly doses of RPT/INH within 16 weeks of treatment initiation.

2. Secondary Outcomes categorized using the RE-AIM framework:

RE-AIM Domain	Outcome
Reach	
 • Proportion of eligible PLHIV offered 3HP who accept to initiate treatment (by age, gender, CD4 stratum, viral load suppression).
Effectiveness/ Cost-effectiveness	
 • Incremental cost of each delivery strategy per disability adjusted life year (DALY) averted. • The incremental health system cost per DALY averted. • The incremental patient cost per DALY averted. • Proportion of participants who initiate 3HP for whom treatment is discontinued due to adverse events or intolerance. • Cumulative 16-month incidence of active TB. • Cumulative 28-month incidence of active TB.

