^a 3HP treatment may last up to 16 weeks^b Patients randomized to choice arm only^c Time-and-motion studies will be performed on 40 randomly selected days (one day per week throughout the year, stratified by day of week). We anticipate that this will capture up to 250 unique participant visits per arm (750 total).^d Patient costing surveys will include 50 participants from each arm, or 150 participants total^e Only if symptomatic, except at end of follow-up.^f 24 participants/arm

Outcome Measures

Primary Outcome (Effectiveness of delivery options)

Outcome	Numerator	Denominator
Proportion accepting and completing 3HP treatment	Number who take at least 11 of 12 doses within 16 weeks of treatment initiation	Number randomized

Secondary Outcomes (Quantitative)

Outcome	Numerator	Denominator
REACH		
Treatment acceptance	Number taking at least one dose of 3HP	Number randomized
EFFECTIVENESS		
Treatment completion	Number who take at least 11 of 12 doses within 16 weeks of treatment initiation	Number taking at least one dose of 3HP

Cost-effectiveness (overall)	(Cost in Arm A – cost in Arm B) from societal perspective	(DALYs averted in Arm A – DALYs averted in Arm B) from societal perspective
Cost-effectiveness (health system)	As above, but from health system/provider perspective	As above, but from health system/provider perspective
Cost-effectiveness (patient)	As above, but from patient perspective	As above, but from patient perspective
Safety	Number for whom treatment discontinued due to adverse events or intolerance.	Number taking at least one dose of 3HP
Cumulative incidence of TB at 16 months	Number diagnosed with TB during 16-month follow-up	Risk set*
Cumulative incidence of TB at 28 months	Number diagnosed with TB during 28-month follow-up	Risk set*
ADOPTION		
All Participants		
Visit Cost Reimbursement	Number of visits for which reimbursement provided on same day	Total number of DOT/refill visits
Time to complete clinic visit	Mean and median number of minutes for each DOT/refill visit	--
SMS or IVR phone call reminders delivered	Number of SMS or IVR phone call dosing or clinic visit reminders delivered	Total number of SMS reminders scheduled to be sent
SMS or IVR phone call reminders following missed appointments	Number of SMS or IVR phone call dosing or clinic missed appointment reminders delivered	Number of participant weeks with 3HP missed appointments
Screening for active TB	Number screened for active TB during DOT visits	Total number of DOT visits

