 3. **Health economic outcomes:** Analysis of health economic outcomes will include 1) a *cost analysis* to estimate and compare the per-patient cost of delivering 3HP under each strategy and 2) a *comparative cost-utility analysis*, to identify the economically preferred option if there is a difference in effectiveness between arms (and the more effective option is also the more expensive one). To identify the preferred option, we will assume a willingness to pay of \$500 per DALY averted (as being comparable to other published studies) in the primary analysis, but will conduct sensitivity

analyses for other thresholds, including inferred thresholds based on Uganda's financing of benchmark TB interventions (e.g., treatment of multi-drug-resistant-TB) as well as traditional thresholds of Uganda's gross national income (**GNI**) per DALY averted.²⁸ For the *cost analysis*, the primary outcome will be a unit cost per patient accepting and completing 3HP under each delivery strategy. We will also describe the major cost components and key drivers of cost (e.g., patient volume or price of 3HP), and conduct sensitivity and scenario analyses around these major cost items to describe the likely variation in per-patient treatment costs across different settings. For patient-level factors, we will use multivariable regression techniques to develop cost functions that describe the relationships between patient-level variables (e.g., gender, distance from clinic) and patient costs under each 3HP delivery strategy.

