**Secondary Objectives:**

1. To estimate the costs and compare the cost-effectiveness of three strategies for delivering 3HP.
2. To identify processes and contextual factors that influence patient acceptance and completion of 3HP under each delivery strategy.
3. To identify clinic-level barriers to adoption and implementation of 3HP under each delivery strategy.
4. To determine the proportion of patients for whom 3HP treatment is discontinued due to adverse events (**AEs**)/intolerance.
5. To determine the cumulative 16-month incidence of active tuberculosis (**TB**) in each arm.

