5. **Health economics outcomes:** Outcomes include the 1) unit cost per patient accepting and completing 3HP under each delivery strategy (cost analysis) and 2) the incremental cost per disability adjusted life year (**DALY**) averted (cost-utility analysis). The cost analysis will estimate and compare the per-patient cost of delivering 3HP under each strategy and; 2) the cost-utility analysis will identify the economically preferred option if there is a difference in effectiveness between arms (and the more effective option is also the more expensive one). To identify the preferred option, we will assume a willingness to pay of \$500 per DALY averted (as being comparable to other published studies) in the primary analysis. We will estimate the incremental cost per DALY averted of patient choice relative to facilitated DOT or SAT.

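### The cost-utility plan names ratios only for choice vs DOT and choice vs SAT, under an undefined effectiveness condition, and gives no rule for deciding among all three strategies

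*SAP*

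**What the plan says.** The SAP's first secondary objective (section 2.1) is "To estimate the costs and compare the cost-effectiveness of three strategies for delivering 3HP".

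SAP 3.7, item 5 splits this into two parts.

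- **Cost analysis.** "The cost analysis will estimate and compare the per-patient cost of delivering 3HP under each strategy". No condition is attached, and all three arms are covered.
- **Cost-utility analysis.** A preferred strategy is to be singled out under this condition: "if there is a difference in effectiveness between arms (and the more effective option is also the more expensive one"). For that purpose "we will assume a willingness to pay of \$500 per DALY averted". The contrasts are then given: "We will estimate the incremental cost per DALY averted of patient choice relative to facilitated DOT or SAT".

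The protocol's Data Analysis section (Health economic outcomes) uses the same condition, "to identify the economically preferred option if there is a difference in effectiveness between arms", with the same cost clause, and names the same two contrasts. It adds sensitivity analyses at other thresholds and a probabilistic analysis by Latin Hypercube Sampling.

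Elsewhere the protocol is broader. The synopsis lists the outcome "Incremental cost of each delivery strategy per disability adjusted life year (DALY) averted". The Outcome Measures table defines the numerator of the ratio generically, as ("Cost in Arm A – cost in Arm B) from societal perspective", without tying either arm to choice.

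Neither document names a DOT vs SAT ratio in its analysis text, ranks the three strategies jointly, gives a dominance or extended-dominance rule, or mentions net benefit. Neither says whether a difference in effectiveness means a significant test, a point estimate, completion or modelled DALYs.

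**The concern.** A clinic can adopt only one of the three strategies as its standard offer. Choosing among mutually exclusive options requires them to be compared jointly, either on a cost-effectiveness frontier or by net benefit at the threshold. Two ratios that both have choice on one side answer a narrower question: whether choice is worth having instead of each alternative. If the answer is no both times, the remaining decision is DOT vs SAT, and the analysis text names no ratio for it.

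The condition raises a second difficulty. When completion differs a little between arms and cost differs a lot, a threshold is needed to weigh one against the other. That is also when a reader could dispute whether the undefined difference exists. At stake is whether the trial can name the economically preferred strategy, which is the stated purpose of the cost-utility analysis.

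**Working it through.** The documents give no cost per arm, DALY total or ratio, so there is no stated figure to reproduce. The check is of the decision logic. Costs and DALYs below are assumed unless a source is given.

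**Measure.** Net monetary benefit per patient at the stated threshold: NB = 500 × DALYs averted − cost.

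**1. What the two contrasts can settle.** Suppose the sign of the net-benefit difference is known for choice vs DOT and for choice vs SAT.

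- Choice beats both: choice is best.
- Choice beats one and loses to the other: the one it loses to is best.
- Choice loses to both: DOT vs SAT is undetermined.

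In 200,000 randomly generated three-arm sets, the two contrasts never picked the wrong arm when choice beat at least one rival. Choice lost to both in 33.5% of sets. That share follows from treating the arms as exchangeable (one in three by symmetry) and is not a forecast for this trial.

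**2. Same planned ratios, opposite answers.**

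| Assumed set | Choice: cost; DALYs | DOT | SAT | Choice vs DOT | Choice vs SAT | NB choice / DOT / SAT | Best |
|---|---|---|---|---|---|---|---|
| B1 | $100; 0.10 | $90; 0.09 | $80; 0.08 | 10/0.01 = $1000 | 20/0.02 = $1000 | −50 / −45 / −40 | SAT |
| B2 | $100; 0.10 | $80; 0.08 | $90; 0.09 | 20/0.02 = $1000 | 10/0.01 = $1000 | −50 / −40 / −45 | DOT |

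In both sets choice is the most effective and most expensive arm, so the SAP's condition is met. The reported pair of ratios is still identical and the preferred arm differs.

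**3. A ratio that is easy to misread.** Assume SAT $40 and 0.10, choice $60 and 0.11, DOT $65 and 0.16.

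- Choice vs SAT: 20/0.01 = $2000.
- Choice vs DOT: (−5)/(−0.05) = $100. Choice is cheaper and less effective here, so a ratio below $500 counts against choice.
- NB: SAT 50 − 40 = 10; choice 55 − 60 = −5; DOT 80 − 65 = 15.
- The deciding ratio, DOT vs SAT, is 25/0.06 = $417, below $500.

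**4. Cost differences when completion is similar.** The protocol's Study Arms and Participant reimbursement text pays about $5-8 per visit, weekly for DOT and at weeks 6 and 12 for SAT. After the day-1 dose, a full course has 11 follow-up visits under DOT and 2 under SAT.

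- At $5: 55 − 10 = $45. At $8: 88 − 16 = $72.
- Equivalent health gain at $500: 45/500 = 0.09 and 72/500 = 0.144 DALY per patient.

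So two arms with nearly equal completion can still differ in net benefit, and a small gain in effectiveness may or may not justify the extra cost.

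**5. The condition, if it were read as a significance test.** This is one possible reading. Inputs are 552 per arm, two-sided alpha 0.025 (SAP 2.5 and 3.4) and an assumed 80% in the comparator. With d the true difference and n = 552, continuity-corrected power is Φ[(d − 1/n − 2.241 × SE0)/SE1], where SE0 is the pooled and SE1 the unpooled standard error.

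| True difference (points) | 2 | 3 | 5 | 7 | 10 |
|---|---|---|---|---|---|
| Probability condition met | 0.07 | 0.15 | 0.45 | 0.79 | 0.99 |

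For 5 points: SE0 = √(2 × 0.825 × 0.175/552) = 0.02287; SE1 = √((0.16 + 0.1275)/552) = 0.02282; (0.05 − 0.00181 − 0.05126)/0.02282 = −0.135, giving 0.45.

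**The case against.** Three stronger readings are tempting, and the documents do not support them.

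- **That the plan restricts itself to the two choice contrasts.** The SAP sentence names two contrasts without excluding a third. SAP 2.4 refers to the protocol for the full description of secondary outcomes, and the protocol defines the ratio for each strategy and for a generic pair of arms. SAP precedence (section 2.3) matters only where the texts conflict. The two named contrasts also match the trial's hypothesis about choice.
- **That a null primary result rules out the cost-utility analysis.** Nothing ties the difference in effectiveness to significance on the primary outcome, and the sentence on estimating the incremental ratio carries no condition. The probabilities in step 5 apply only under one reading.
- **That joint uncertainty in cost and effect is thrown away.** The protocol plans, without condition, a probabilistic analysis that varies all parameters together.

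There is more to be said for the plan. The full condition describes a trade-off, which is where a threshold is needed. If the more effective arm is cheaper, it dominates. If effects are equal, the unconditional three-arm cost comparison shows the cheapest arm. The DOT vs SAT ratio also follows by subtraction when increments are reported separately: in step 3, (20 + 5)/(0.01 + 0.05) = $417. And the numerical examples are constructed.

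All of this stands, and it limits the point. It does not remove it. Being able to derive a ratio is not a stated rule for using it. Near-equal effects and extended dominance are covered neither by obvious dominance nor by the cost comparison. No three-way output, such as the probability that each strategy is optimal, is attached to the probabilistic runs.

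**Conclusion.** The point holds as a gap in the decision rule. No data or model output is lost. The two named ratios fail to identify the preferred strategy in one situation: choice has lower net benefit than both DOT and SAT at $500. How likely that is cannot be judged from the documents. Separately, when effectiveness is similar but not equal, the undefined condition may leave no option named although costs differ. The visit reimbursement gap of $45-72 per full course shows that such a difference is realistic. That figure assumes every scheduled visit is attended and paid. It counts reimbursement only, so it is not an estimate of the full cost difference, and the choice arm would depend on the mix of modes chosen.

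This concerns a secondary, model-based analysis and does not affect the primary comparison. It should still be corrected, because the stated objective is to compare three strategies.

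**What to change.** In SAP 3.7, item 5, and in the protocol's Health economic outcomes text:

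1. Remove the condition, so that the preferred option is identified whatever the effectiveness result.
2. Order all three strategies by cost. Remove dominated and extendedly dominated ones, and report each remaining ratio against the next non-dominated strategy. State that DOT vs SAT is included.
3. Report incremental costs and incremental DALYs separately alongside every ratio, so that a cheaper and less effective comparison is recognisable.
4. Report net monetary benefit for each strategy at $500, and the probability that each is optimal, from the Latin Hypercube runs already planned. Repeat this at the alternative thresholds the protocol already lists.

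This needs no new data, participants or model runs; it changes only what is reported from the same output. Label: free improvement.

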### 3.8 Interim analysis

1. **Background:** The decision to conduct an interim analysis of trial data and the type of analysis was determined by the Trial Steering Committee (**TSC**), comprised of 3 members not involved in the implementation of the trial nor on the investigative team, and without the Principal Investigators seeing outcome data disaggregated by study arm
2. **Statistical Analysis:** Determination of the timing and the contents of the interim analysis was made in consultation with the study statistician and with input from the TSC. We will calculate and report the proportion (and 95% CI) of patients accepting and completing 3HP treatment within 16 weeks of randomization, aggregated across all study arms. Selected secondary outcomes may also be reported and include treatment acceptance and occurrence of severe adverse events resulting in stopping of 3HP treatment. We will assess outcomes stratified by sex, age, and time on ART. Secondarily, we will take a Bayesian inference approach to estimate the posterior probability that the proportion of patients who accept and complete 3HP, denoted here as  $\theta$ , exceeds 80% in at least one of the three study arms. We will use a Beta distribution to the outcome parameter  $\theta$  and a non-informative flat prior, Beta(1,1), making it such that the prior has little influence on the posterior distribution. We will calculate the posterior probability that  $\theta$  exceeds 0.8 by calculating the size of the tail of the posterior distribution that is above 0.8.

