All interested participants who meet eligibility criteria and consent to be included in the study will be randomized via a computer-generated algorithm to one of three arms: facilitated DOT, facilitated SAT, and patient choice between facilitated DOT and facilitated SAT (with the help of a decision aid tool). Randomization will be performed using computer-generated random permuted blocks of variable size between 9, 12 and 15, with an equal allocation ratio between the three arms. Randomization numbers will be generated using a statistical software package and individual random assignment sheets will be placed and sealed in opaque envelopes in batches of multiple blocks to minimize predictability that would occur if single blocks were used. Generation of randomization numbers and their concealment will be done by a US-based Study Biostatistician who will not have contact with participants. The numbers will be passed on to the local Study Biostatistician for custody and onward transfer to Study Coordinator in numbers corresponding to the expected enrolments for given time periods. Accountability for released randomization number containing envelopes will be given prior to release of subsequent ones. Each eligible participant will be asked by a Study Coordinator or his/her designee to select an envelope which s/he will open to see the randomization number and study arm. This will help to avoid/mitigate participants from accusing the research team of selecting for them a study arm. All randomization numbers will be monitored daily by the Study Coordinator and weekly by the local Biostatistician and fortnightly by the US-based via a database at a data management center. Recruitment will be continued until 1656 participants are randomized and offered treatment (expected to be completed within 2 years).

Study Procedures (See Table 2 and Figure 1)***Day 1 (day of enrollment)***

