## 2.5 Sample Size

We estimated our sample size for the primary outcome (N=1656; 552/arm) based on a minimum clinically important difference of 10% in 3HP completion, comparing patient choice vs. DOT arms. Of note, the Centers for Disease Control and Prevention (**CDC**) TBTC iAdhere study of 3HP delivery strategies chose a 15% non-inferiority margin between DOT and SAT based on cost-effectiveness modeling in the US. We chose 10% to be more conservative because similar modeling studies have not been done in low-income settings, and because ours is not a non-inferiority design. To be maximally conservative, we applied a Bonferroni correction based on two independent comparisons (choice vs. DOT and choice vs. SAT). Assuming a two-sided alpha of 0.025, and 5% loss between consent and allocation, a sample size of 552 participants per arm (N=1656 total) is required to provide power of 0.90 to detect this difference (Table 3). This sample size will also give us power of 0.85 to detect a point estimate of at least 80% effectiveness in the patient choice arm, assuming a true effectiveness of 85%. If the true effectiveness rises to 86%, our power to show effectiveness >80% increases to 0.96. Power was calculated using the PS - Power and Sample Size program.

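### SAP 3.8 asks for the probability that at least one arm exceeds 80%, but the single Beta tail it prescribes does not compute that probability

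*SAP*

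**What the plan says.** SAP 3.8 item 2 has two parts. The main interim summary is the proportion accepting and completing 3HP with a 95% CI, "aggregated across all study arms". A secondary Bayesian step then seeks the posterior probability that the same proportion, called theta, "exceeds 80% in at least one of the three study arms".

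For that step the SAP assigns theta "a non-informative flat prior, Beta(1,1), making it such that the prior has little influence on the posterior distribution". It obtains the probability "by calculating the size of the tail of the posterior distribution that is above 0.8".

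Item 1 of the same section says that the interim was decided by the Trial Steering Committee, "without the Principal Investigators seeing outcome data disaggregated by study arm". SAP 3.8 gives no interim sample size, no posterior threshold and no decision rule.

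**The concern.** The target is a statement about three proportions: at least one of theta_DOT, theta_SAT and theta_Choice lies above 0.80. The method is a statement about one proportion. A single tail of a single Beta posterior cannot be the probability of a union of three events unless it is known which data enter and how the arms are combined, and the SAP says neither.

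Two programmers could follow the text faithfully and report very different numbers. One would pool the arms, as the preceding summary does. The other would compute a tail for each arm and then have to invent a combining rule. The committee would receive a figure on the 80% hypothesis (SAP 2.2, hypothesis 2) without knowing which question it answers.

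**Working it through.** The plan states no posterior value here, so there is no figure to reproduce. The check compares the stated method with the stated target.

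**Inputs**
- Threshold 0.80 and prior Beta(1,1): SAP 3.8.
- Equal arm sizes: the protocol's Randomization section specifies allocation "with an equal allocation ratio between the three arms".
- Interim n per arm: not given. Assumed 100 to 552, where 552 is full enrolment per arm (SAP 2.5).

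**Formulas**, with x_k successes among n in arm k and X = x_1 + x_2 + x_3:
- Arm tail: P_k = P(Beta(x_k + 1, n - x_k + 1) > 0.8)
- Pooled tail: P(Beta(X + 1, 3n - X + 1) > 0.8)
- At least one arm (the union), with independent priors: 1 - (1 - P_1)(1 - P_2)(1 - P_3)

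**Before any data.** One flat prior puts 1 - 0.8 = 0.20 above the threshold. Three independent flat priors put 1 - 0.8³ = 0.488 on the union.

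**Worked example: observed 70/75/85%, assumed n = 200**
- Successes are 140, 150 and 170, so X = 460 of 600.
- Arm tails: Beta(141, 61) gives 0.0003, Beta(151, 51) gives 0.0375, Beta(171, 31) gives 0.960.
- Union: 1 - 0.9997 × 0.9625 × 0.040 = 0.961.
- Pooled tail: Beta(461, 141) gives 0.021.

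**Same observed rates at other assumed sizes**

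| n per arm | Pooled tail | Union |
|---|---|---|
| 100 | 0.071 | 0.893 |
| 200 | 0.021 | 0.961 |
| 276 | 0.009 | 0.984 |
| 400 | 0.002 | 0.994 |
| 552 | 0.0004 | 0.9985 |

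**Averages over simulated interims, true rates 85/75/75%** (100,000 per setting). The pooled tail averages 0.30 at 100 per arm and about 0.11 at 552; the union averages 0.87 and 0.985. The true average rate is (85 + 75 + 75)/3 = 78.3%, so more data push the pooled tail towards 0 and the union towards 1.

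**Per-arm tails without a combining rule.** With 80% observed in every arm and n = 200, each tail is 0.472, while the union is 1 - 0.528³ = 0.853. Three uncombined tails, or the largest of them, are therefore not the stated quantity either. The largest tail comes close only when a single arm is near or above 80%, as in the worked example (0.960 against 0.961).

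**Reference value for the union.** If every arm is truly at 80%, each P_k is roughly uniform, so the union averages about 1 - 0.5³ = 0.875. Simulation gives 0.86 to 0.87 across 100 to 552 per arm.

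**The case against.** The strongest defence is that the text can be read as one theta per arm, with the prior and tail step repeated for each. The word about aggregation belongs to the preceding summary, and the Bayesian step opens separately. That reading is fair, and it means a wrong computation is not established. It still leaves out the rule that turns three tails into one probability, so the same text change is needed.

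A second defence is that the pooled tail is not meaningless. The pooled proportion is an average of the arm rates, so if it exceeds 0.80 at least one arm must. The pooled tail is thus a conservative lower bound, and it suits an interim in which arm-level outcomes are kept from the Principal Investigators. This also stands, but a bound of 0.02 for a probability of 0.96 would mislead a committee that reads it as the probability itself.

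A reader might go further and infer that the union, once computed properly, is inflated because it takes the best of three arms. The documents do not support calling that an error. Under independent priors the union is the correct posterior for the event the SAP names, and it must be at least as large as any one arm's tail. It does exceed 0.95 in 38 to 40% of simulated interims when every arm is exactly at 80%, but that is the boundary case and the 0.95 cut-off is not the SAP's. With every arm at 78%, the mean union depends strongly on n (0.72 at 100 per arm, 0.49 at 552), and it exceeds 0.95 in 14% and 2% of interims respectively. What does stand is that the prior value of 0.488 and the boundary value of about 0.87 go unmentioned, so a reader could misjudge a moderately high figure.

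A reader might also infer harm to the trial's error rate. SAP 3.8 attaches no threshold or stopping rule, and the final 80% assessment in SAP 3.4 uses its own Bonferroni-corrected exact interval. No effect on the final tests can be derived.

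**Conclusion.** The point holds as a mismatch between target and method. The named event is a union over three arms, and the prescribed calculation, whether read as pooled or as per-arm, does not yield its probability. The pooled reading is plausible given the adjacent text, and it can reverse the message when one arm does well and the others do not.

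The sizes rest on assumed interim numbers of 100 to 552 per arm, equal arms, and independent Beta(1,1) priors for the union. The gap depends on the pattern of rates. The consequence is confined to a secondary interim figure given to the steering committee, so this should be corrected but does not threaten the primary analysis.

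**What to change.** In SAP 3.8 item 2:

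1. Define theta_DOT, theta_SAT and theta_Choice, each with an independent Beta(1,1) prior.
2. State that arm-level data are used, and compute P_k = P(theta_k > 0.80) for each arm.
3. Compute the at-least-one-arm probability as 1 - (1 - P_1)(1 - P_2)(1 - P_3).
4. Report it beside two reference points: its prior value of 0.488, and its average of about 0.87 when all arms are exactly at 80%.
5. Restrict arm-level values to the steering committee and the unblinded statistician, so that the Principal Investigators stay blinded by arm.

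If the interim must stay pooled, restate the target as the probability that the pooled proportion exceeds 0.80 and remove the at-least-one-arm wording.

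Either route costs a few lines of SAP text and code. The first also requires that someone other than the Principal Investigators handles the arm-level output.
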